With the Research Methods Core, Drs. [name] and [name] will standardize data between clinics to the extent possible and determine the best approach to create a pooled dataset. Baseline EHR data collection will commence immediately after randomization. Follow-up data collection will be conducted after the 1-year study period is complete.

Clinic level - patient volume (number of active adult patients aged 18+ years during the 12-month study period, total number of primary care clinic visits), number of PCPs, and number of patients at risk of ADRD (active patients aged 55+ with no prior ADRD diagnosis), total number of visits, visits by PCP and provider type, and aggregate counts of new diagnoses (MCI, ADRD, other dementia) based on the ICD-10 codes for these diagnoses. Total patient volumes for patients aged 55-64 and 65+ will be used for clinic-based calculations of the cumulative incidence and prevalence of MCI, ADRD, and dementia.

Patient Level - The goal of this analysis is to determine whether patients with diagnosed ADRD received healthcare consistent with current quality of care standards. Eligible clinic patients are active clinic patient with prevalent ADRD as of the first day of the 12-month baseline [or follow-up] surveillance interval, age 55 or older at the start of the surveillance interval, at least one primary care clinic visit during the 12-month baseline [or follow-up] surveillance interval.

Data extraction domains

- 1. Demographics age, sex, marital and employment status/income, education, language(s) spoken, health insurance
- 2. Comorbidities hypertension, type 2 diabetes, hyperlipidemia, obesity, heart disease, stroke, sleep apnea, and smoking
- 3. Neuroimaging orders

- 4. New prescriptions for potentially beneficial drugs for ADRD symptoms (e.g., cholinesterase inhibitors, N-methyl-D-aspartate antagonists, antidepressants, and antipsychotics) in clinics that track such information in their EHR.
- 5. ADRD quality of care measures, as reported during the Clinic Profile Interview with clinic directors or administrative leadership.
- 6. Quality of care outcomes will be based on existing quality indicators. These comprise 5 domains of care for patients diagnosed with dementia: annual cognitive assessments, annual evaluation of functional status, annual behavioral and psychiatric screening, advance care directives, pharmacological treatment changes.

Manual Medical Chart review

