The manual chart review (MCR) will serve to capture details that cannot be extracted from the EHR, and to validate accuracy of patient-level EHR data. It will be conducted once at the 12 month follow-up and will cover both the baseline and 12-month follow-up timepoints for a random selection of at least 20 patients per clinic per time point to 1) document ADRD screening rates and 2) ascertain whether patients with diagnosed ADRD had the quality of care outcomes listed in data collection table above.

- 10 randomly selected patients eligible for cognitive screening will be reviewed to document ADRD screening rates within the EHRs at each site. Screening for MCI or dementia (e.g., Mini-Cog or AD8) may not be captured if the PCP does not use Annual Wellness Visit, Cognitive Assessment and Care Planning, Advanced Care Planning, or Neurobehavioral Status Exam CPT codes.
- 10 randomly selected patients with a previous dementia diagnosis will be examined to assess healthcare quality metrics such as completion of advanced directives, which are not always captured by the Advanced Care Planning CPT codes.

INTACT Intervention

The INTACT Intervention has two components: 1) provide a training for Primary Care Providers (PCPs) training in screening, diagnosis, and care for ADRD and 2) at the clinic level provide a workflow model for cognitive evaluation and setting a plan for the newly diagnosed patient. The INTACT intervention lasts 12 months and Continuing Medical Education credits will be available to PCPs who complete the INTACT training program.

Part 1 PCP training

The INTACT program is composed of 5 online sessions, 4 quarterly webinars and a resource packet. The intervention will be delivered over a period of 12 months, 5 PCP training sessions are designed to be delivered over four months.

Training Sessions

INTACT PCP online training program has 3 didactic sessions and 2 additional sessions focusing on the implementation of the training content in the clinic's unique operational and clinical workflow.

- Session 1: Make a diagnosis of cognitive impairment. An efficient framework for evaluating memory and other cognitive concerns in the primary care setting
- Session 2: Set a plan for the newly diagnosed patient. Structure a discussion about a new diagnosis of mild cognitive impairment including words to use, talking about prognosis, and how to provide high quality community resources to support patients and families.

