We will use hierarchical regression models with a random intercept for clinic; model specification will reflect that all PCPs within a clinic share the same intervention status. Linear hierarchical models will be used for continuous outcomes and logistic hierarchical models for binary outcomes. The intervention effect will be interpreted as the fixed effect for the INTACT × time (baseline vs. follow up) interaction. We will analyze PCP-specific outcomes using 2 approaches: a within-PCP change analysis and a within-clinic change analysis. For the analysis of within-PCP change, we will restrict the dataset to PCPs who participate in both baseline and follow-up data collection. These models will specify longitudinal data with 2 time points per PCP. Here, the INTACT × time interaction term will be interpreted as the intervention's effect on individual PCPs over time. For the analysis of within-clinic change, the dataset will include all PCPs who participate in data collection at baseline or follow-up regardless of whether they participate in both. The INTACT × time interaction term will be interpreted as the intervention's effect on the clinic environment. Primary analysis will not adjust for covariates. Secondary analyses will adjust for the same set of clinic covariates selected a priori, as above, and for clinic- and PCP-level covariates observed to be unbalanced between groups by chance alone.

Clinic Outcomes (Aim 3)

Incidence rates of new MCI, ADRD, and other dementia diagnoses will be estimated at each clinic for the 12-month intervention period using HER data. All patients aged 55+ who are at risk of the outcome during the study will be included. Poisson regression models will be used to estimate the effect of the intervention on changes in diagnosis rates for MCI, ADRD, and other dementia between intervention and control arms. Poisson models will include number of person years as an offset term. We will be parsimonious in our choice of adjustment variables, but will consider patient volume, state, and type of

facility if an imbalance is apparent after randomization. If we find evidence of an imbalance in covariates between study arms, we will adjust for those variables in the regression analysis.

Patient Outcomes (Aim 3)

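### Patient volume, a candidate adjuster for the diagnosis-rate model, is defined over the year after randomisation; it should be fixed as a pre-randomisation value

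*Combined protocol and SAP*

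**What the plan says.** The Clinic Outcomes (Aim 3) section estimates rates of new MCI, ADRD and other dementia diagnoses at each clinic over the 12-month intervention period. It uses Poisson models with a person-years offset. On adjustment it promises parsimony, "but will consider patient volume, state, and type of" and, continuing after a page break, "facility if an imbalance is apparent after randomization". The next sentence is firmer: "If we find evidence of an imbalance in covariates between study arms, we will adjust for those variables in the regression analysis". No threshold for imbalance is given, and no measurement window is named for any adjuster.

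The EHR data Extraction section, in its clinic-level list, holds the only definition of the first adjuster: "patient volume (number of active adult patients aged 18+ years during the 12-month study period, total number of primary care clinic visits".

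Three statements fix the timing:
- Under EHR data Extraction: "Baseline EHR data collection will commence immediately after randomization".
- In the same paragraph: "Follow-up data collection will be conducted after the 1-year study period is complete".
- Under INTACT Intervention: "The INTACT intervention lasts 12 months".

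**The concern.** An adjuster in a randomised comparison should be a quantity that the intervention cannot have changed. INTACT trains PCPs to evaluate cognition and gives clinics a workflow for doing so, so extra visits in the intervention arm are a plausible consequence. If volume is measured in that year, two things go wrong. A difference between arms in volume cannot be read as chance imbalance, because it may be an effect of INTACT. Adjusting for it then removes whatever part of the effect on diagnosis rates runs through volume.

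At stake is the estimate for new diagnoses, the main clinic-level outcome. The Power section covers only PCP-level and patient-level outcomes, so the plan offers no stated precision for this one.

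**Working it through.** **Step 1. Which year is the study period?** Four places agree:
- Study Design overview: wait-list clinics may receive INTACT once the 1-year study period is over.
- Note on immediate intervention arm engagement (under Randomization): PCPs employed at any time in the study period are invited to take part in the intervention.
- EHR data Extraction: follow-up extraction comes after the study period ends.
- INTACT Intervention: the programme also lasts 12 months.

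So the study period is the year after randomisation, and it coincides with the outcome window in Clinic Outcomes (Aim 3).

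**Step 2. Is the wording deliberate?** In the same section, the patient-level eligibility text names a baseline or follow-up interval. The patient-volume definition names only the study period. An analyst following the text would take the post-randomisation value.

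**Step 3. Possible size.** The plan gives no figure to reproduce here, so every input below is an assumption. Let d be the log rate ratio not acting through volume, g the effect of INTACT on log volume, and b the slope of the log diagnosis rate on log volume.
- Total log effect = d + b × g.
- Log effect after adjusting for study-year volume = d.
- Share removed = b × g / (d + b × g).

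With d = 0.30:
- g = 0: share removed 0, whatever b is.
- g = ln(1.03) = 0.030, b = 0.5: b × g = 0.015, about 1.5% on the rate ratio. Share = 0.015 / 0.315 = 5%.
- g = 0.10, b = 0.5: 0.05 / 0.35 = 14%.
- g = 0.20, b = 1.0: 0.20 / 0.50 = 40%.

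The large values need a large effect on total volume. Volume counts all adults aged 18 or over and all primary care visits, whereas the diagnosis outcome concerns patients aged 55 or over. Any effect of INTACT on visits is therefore diluted, and the lower end is more credible.

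**Step 4. State, for the caution only.** The number of states S is not given. Assume 28 clinics, 14 per arm, randomised in pairs without regard to state, with S state fixed effects in a linear clinic-level comparison of follow-up values.
- Residual df = 28 − 1 − S, against 26 without state.
- Variance inflation = 7 / (arm sum of squares left after state), where 7 = 28 × 0.5 × 0.5.

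Medians over 4,000 simulated allocations for each S:
- S = 2: 25 df, 1.02.
- S = 3: 24 df, 1.06.
- S = 4: 23 df, 1.10 (1.11 under some spreads of clinics over states).
- S = 8: 19 df, 1.33; interval about 1.18 times as wide; about 5 clinics in states with one arm only.
- S = 10: 17 df, 1.48; interval about 1.25 times as wide; about 7 such clinics.

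**The case against.** The best reply is that baseline volume is what the team means. A baseline extraction is planned. The Patient Outcomes (Aim 3) section speaks of covariates unbalanced at baseline, and PCP Outcomes (Aim 2) of imbalance by chance alone. The study-period wording sits in a list of extraction fields, not in the analysis section. This stands as a possible reading, and it is why the point says that the analysis could use the later value, not that it will. It does not close the gap: those two sentences concern other outcomes, and neither changes the only definition of patient volume.

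A second reply is that the bias is minor and rests on invented inputs. That also stands, and it limits the weight of the point.

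A third is that the section also speaks of changes in diagnosis rates. If change were modelled as an arm-by-time interaction, a single volume value per clinic entered as a main effect would largely leave the interaction alone. A value for each year would not, and the section describes rates for the intervention year only.

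A reader might go further and infer that state has too many levels for 28 clinics. The documents do not support that:
- The number of states is stated nowhere, and at 2 to 4 states the cost is negligible.
- The plan promises parsimony and sets no imbalance threshold, so it is not established that state would enter.
- The loss needs a follow-up-only comparison. In a linear arm-by-time model with 10 states, the interaction's variance factor is 4 × (1/14) = 0.2857 with or without state terms.
- Adjusting for state could also remove real variation between states, which these figures do not credit.

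**Conclusion.** The point holds for patient volume, as a minor correction. The plan's only definition places it in the intervention and outcome year, and nothing in the analysis text ties the adjuster to an earlier window. The bias is probably small: about 1.5% on the rate ratio under modest assumptions, zero if INTACT does not change volume, and larger only if it changes total clinic volume substantially. The documents supply none of these inputs. The point also assumes that volume is used at all, since adjustment is conditional, and that the model compares follow-up rates or uses each year's own volume.

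The documents do not show that state is an unsuitable adjuster. If about 8 or more states take part and the model compares follow-up rates between arms, state fixed effects would raise the variance by about 1.3 times or more. At 2 to 4 states the factor is 1.02 to 1.11. Whether to replace state with something coarser, such as urban or rural setting, is a trade-off on which statisticians could differ.

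**What to change.** In Clinic Outcomes (Aim 3), add that patient volume, for both the imbalance check and any adjustment, is the pre-randomisation value and never that of the intervention year. The source can be either of two:
- the baseline EHR extract, stated to cover the 12 months before randomisation (the query runs just after randomisation, so its window must be written down);
- the clinic and patient population form completed before randomisation, if it records volume; the documents do not describe its contents.

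In the same paragraph, say how state would be coded or grouped if used, and fix this before any outcome data are seen.

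The cost is a sentence or two. No new data source is needed, and baseline volume uses the same single degree of freedom as study-year volume.
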